8.5 Counting Rules for Efficacy Analysis

The counting rules for computing proportions for efficacy endpoints are laid out in this section. For any endpoint under consideration, the end of the event-counting period will first be determined for each subject. If a subject has at least one episode of the event during this event-counting period, then he/she will be included in the analysis and the episode with the most severe grade will be counted. If there are multiple episodes with the same severity (grade), then the calendar date of the occurrence of the first such event will be counted. For example, if a subject had multiple episodes of a given event of varying degrees of severity, for the purpose of estimating time to event the first occurrence will be used; however, for tabulation of severity, the highest grade event will be included.

8.6 Conventions for Descriptive Summaries

For the descriptive summaries of BP parameters and laboratory analytes of interest (e.g. individual components of the fasting lipid profile and measures of renal function) at any given time point: If a subject has more than one measurement recorded during the corresponding time-window, the result closest to the target day for that time point will be used. In any case in which both observations are equidistant from the target day, the later measurement will be used. Above convention will be followed unless noted otherwise.

8.7 Safety Data Conventions

Safety data will be handled according to the BMS safety data convention standards and Supplement to Safety Guidelines for BMS-224818.

* Laboratory AE's are clinically significant laboratory values per the assessment of the investigators as reflected in the adverse event records.

8.9 Missing, Unknown or Partial Dates

No imputation of event dates will be performed on any efficacy endpoints, including acute rejection, graft loss, death, laboratory measures and blood pressures, with the exception of cases wherein the onset date of an episode related to acute rejection is unknown; in such cases, the date of the first biopsy for that episode will be used as the onset date of the episode.

Missing Start Dates of study therapy

No date imputation will be done for missing start dates of study therapy.

Missing Start Dates of concomitant medications

If start date is missing then it will be imputed differently depending on whether the consent date is available or not. If the consent date is available then the start date will be imputed by the consent date. Otherwise, the start date will be imputed as 01 January 1900.

Partial Start Dates of concomitant medications

If a partial start date is available then it will be imputed by the earliest possible date based on the partial start date. For instance, if the available partial start date is Year 2005, then the imputed start date will be 01 January 2005. However, if the available partial start date is May 2005, then the imputed start date will be 01 May 2005.

Missing or Continuing Stop Dates of concomitant medications

If a stop date is missing or treatment is continuing then it will be imputed as 31 December 2099.

Partial Stop Dates of concomitant medications

If a partial stop date is available then it will be imputed by the latest possible date based on the partial stop date. For instance, if the available partial stop date is Year 2005, then the imputed stop date will be 31 December 2005. However, if the available partial stop date is May 2005, then the imputed stop date will be 31 May 2005.

Missing or Partial Onset Dates of Adverse Events

Before imputing any missing or partial onset dates, two new dates will be defined: a surrogate date for each onset date (missing or partial), and an earliest possible date (EPD) for each partial onset date. The surrogate date will be defined as the first non-missing valid date from the following list (in order of precedence):

- First active study medication date of any study medication,
- informed consent date, or
- visit date corresponding to the visit at which the event was reported if a valid non-missing date is not available for any of these dates, the surrogate date will be set to missing.

[figure not shown]
The EPD is based on the partial onset date itself. For instance, if the available partial start date is Year 2005, then the EPD will be 01 January 2005. However, if the available partial start date is May 2005, then the EPD will be 01 May 2005.

If the onset date is missing, then the imputed onset date will be the surrogate date as defined above. If the surrogate date is missing, then the imputed onset date will be the visit date.

If the onset date is only partially available, the imputation of the onset date will follow different rules depending on whether the surrogate date is missing or not. Partial date imputation is

illustrated in the following diagram. (If the surrogate date is missing, then the imputed onset date will be the EPD. If the surrogate date is not missing, then the imputed onset date will depend on whether the EPD is earlier than the surrogate date or not. If the EPD is not earlier than the surrogate date, then the imputed onset date will be the EPD. Otherwise, the surrogate date will be used as the imputed onset date provided the surrogate date is consistent with the partial onset date. If the surrogate date is inconsistent with the partial onset date, then the imputed onset date will be the latest possible date based on the partial onset date.)

Figure 8.9-1: Missing or Partial Onset Dates of Adverse Events

9 CONTENT OF REPORTS

The results of this study will be presented in a standard BMS Clinical Study Report (CSR). Key results and any unanticipated findings that are unusual for this study will be identified. A meeting for the initial dissemination of study results will be held after database lock. Attendees at this meeting will review all efficacy and safety summaries and listings and will identify key results that should be highlighted in the CSR.

APPENDIX 1 LIST OF ABBREVIATIONS

Table 9-1: List of Abbreviations

Term	Definition
AE	Adverse Event
AR	Acute Rejection
BPAR	Biopsy proven AR
BMS	Bristol-Myers Squibb
BMS-224818	LEA29Y (belatacept)
BP	Blood Pressure
BUN	Blood Urea Nitrogen
cGFR	calculated Glomerular Filtration Rate
CI	Confidence Interval
CMV	Cytomegalovirus
CNI	Calcineurin inhibitor
CRF	Case Report Form
CsA	Cyclosporine A (cyclosporin)
CSR	Clinical study report
DBP	Diastolic Blood Pressure
DMC	Data Monitoring Committee
DSA	Donor Specific Antibodies
EBV	Epstein-Barr virus
EC-MPS	Enteric-coated Mycophenolate Sodium
GFR	Glomerular Filtration Rate
HbA1c	Hemoglobin A1c
HDL	High-density lipoprotein
HLA	Human Leukocyte Antigen
HUS	Hemolytic Uremic Syndrome
Ig	Immunoglobulin
ITT	Intent-To-Treat
IVRS	Interactive Voice Response System
LDL	Low-density lipoprotein
MedDRA	Medical Dictionary of Drug Regulatory Activities
MMF	Mycophenolate mofetil
MPA	Mycophenolic acid
MDRD	Modification of Diet in Renal Disease (study)

Table 9-1: List of Abbreviations

Term	Definition
MTSOSD-59R	Modified Transplant Symptom Occurrence and Symptom Distress Scale-59R
NODAT	New Onset Diabetes After Transplantation
NULOJIX	Commercial belatacept
PD	Pharmacodynamics
PK	Pharmacokinetic(s)
PML	Progressive multifocal leukoencephalopathy
PTLD	Post-Transplant Lymphoproliferative Disorder
SAE	Serious Adverse Event
SBP	Systolic Blood Pressure
SCr	Serum Creatinine
TAC	Tacrolimus
TG	Triglyceride
UPCR	Urinary protein/creatinine ratio

APPENDIX 2 RELEVANT PROTOCOL DEVIATION CRITERIA

Table 9-2: Relevant Protocol Deviation Criteria

Per-Protocol Deviation Code	Per-Protocol Deviation	Type
1.	Recipients with EBV serostatus negative or unknown	Serious Breach
2.	Genetically-identical donor recipient pairs (i.e., identical twins)	Serious Breach
3.	
 • Subjects with previous graft loss due to AR • Subjects with a positive T-cell or B-cell cross match • Recipients of extended criteria deceased donor (ECD) kidney, as defined in the protocol • Subjects receiving paired (dual or en bloc) kidney transplants 
 • CMV-negative subjects scheduled to receive a kidney from a CMV-positive donor • Subjects with a past history of or current need of desensitization therapy 	Subject Violation
4.	
Any of the following conditions apply:
 
 • Subjects with a recent (within 3 months prior to transplant) PRA \geq 20% • Donor age < 10 years Recipient age < 18 or > 75 at screening 	Serious Breach
5.	
Subjects with underlying renal disease of:
 
 • Primary focal segmental glomerulosclerosis 
 • Type I or II membranoproliferative glomerulonephritis 
Atypical hemolytic uremic syndrome (HUS) / thrombotic thrombocytopenic purpura
	Serious Breach
6.	
Any of the following conditions apply:
 
 • Subjects receiving maintenance immunosuppressive agents for other indications, such as 	Subject Violation

Table 9-2: Relevant Protocol Deviation Criteria

Per-Protocol Deviation Code	Per-Protocol Deviation	Type
7.	treatment of autoimmune disease. 
 • Subjects received treatment other than assigned study medication Subjects with Body mass index (BMI) > 35kg/m ² for non-diabetic and >30kg/m ² for diabetic subjects at screening	Serious Breach

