### **3.3.2      *Exclusion Criteria***

**Subjects meeting the following criteria are prohibited from entry into the study.**

#### **1. Target Disease Exceptions**

- a) Subjects who are seronegative for prior exposure to EBV or those whose EBV serologic status is unknown at randomization.
- b) Genetically-identical donor recipient pairs (ie, identical twins)
- c) Subjects with a recent (within 3 months prior to transplant) PRA  $\geq 20\%$
- d) Subjects with a past history of, or current need for desensitization therapy
- e) Subjects with previous graft loss due to acute rejection
- f) Subjects with a positive T-cell lymphocytotoxic cross match or any detectable donor specific antibodies prior to transplantation
- g) Recipients of kidneys from donors  $< 10$  years old
- h) Recipients of an extended criteria donor (ECD) kidney, defined as:
  - i) Donors  $\geq 60$  years old, or
  - ii) Donors aged 50 – 59 years with any 2 of the following:
    - death from cerebrovascular accident;
    - hypertension;
    - serum creatinine  $> 1.5$  mg/dL; or
  - iii) Not applicable per Protocol Amendment 03
  - iv) Recipients of kidneys donated after cardiac death
- i) Subjects with prior or concurrent, non-renal solid organ or cell (e.g., pancreas, kidney-pancreas, or islet cell or stem-cell) transplants, and those deemed by the Investigator as being likely to require a non-renal transplant in the next 3 years
- j) Subjects receiving paired (dual or en bloc) kidney transplants
- k) CMV-negative subjects scheduled to receive a kidney from a CMV-positive donor

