#### **2. Medical History and Concurrent Diseases**

- a) Subjects with ESRD due to any of the following underlying chronic renal diseases:
  - Primary focal segmental glomerulosclerosis (FSGS)
  - Type I or II membranoproliferative glomerulonephritis (MPGN)
  - Hemolytic uremic syndrome (HUS) / Thrombotic Thrombocytopenic Purpura

If a subject has ESRD of unknown etiology and/or has no histologically-confirmed underlying diagnosis, the subject may be enrolled into the study if, in the opinion of the Investigator, the patient's prior clinical, laboratory, and/or radiographic findings are unlikely to be consistent with any of the above diagnoses.

- b) Hepatitis C virus (HCV): Subjects or donors known to be positive for anti-HCV antibody, or for HCV RNA detectable by polymerase chain reaction (PCR)
- c) Hepatitis B virus (HBV): subjects or donors known to be positive for hepatitis B surface antigen or for HBV DNA detectable by PCR
- d) Human immunodeficiency virus (HIV): subjects or donors known to be HIV positive
- e) Subjects with current evidence or past history of active or inadequately\* treated latent TB infection. Subjects must have documentation of negative screening for active and latent TB infection to be eligible for randomization\*, specifically:
  - i) A chest x-ray (posterior-anterior and lateral views) that is negative for radiographic evidence of pulmonary TB within the last 6 months prior to transplant.
  - ii) A negative screening test for latent TB infection (LTBI) [intradermal PPD, or interferon-gamma release assay (IGRA) such as QuantiFERON® TB Gold test or T-Spot-TB] that was performed *at any time* prior to the current transplant.
    - (1) Those subjects who do not have a documented negative result, specifically from an IGRA test performed within the last 3 months prior to randomization, **must** be screened for LTBI with an IGRA test performed during the Screening Visit.

\*Notes:

- ◆ For this protocol, "adequately treated" LTBI is defined as completion of a standard course of antimicrobial therapy per a local standard of care, e.g., for the U.S., recent CDC guidelines.
- ◆ Results of the Screening Visit IGRA are not required for randomization when the results from a historical negative screening test (PPD or IGRA) are available [see (2) (e) (ii) above].

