## 8.2 Populations for Analyses

- The primary endpoint will be initially assessed on the ITT population in each treatment group. The ITT population will consist of all randomized and transplanted subjects treated with at least one dose of Thymoglobulin and one dose of study treatment, either belatacept or TAC, and will be included in the safety and efficacy analysis data sets. In these analyses, CSBPARs occurring after discontinuation from assigned therapy will be counted in the treatment arm to which the subject was originally randomized.
- Additionally, for CSBPAR, a sensitivity analysis will be performed with right censoring at the time of discontinuation from the assigned therapy.
- An as-treated analysis will be based on the treatment regimen received. Analysis of treatment differences in the rates of CSBPAR will only include those subjects who remain on their original therapy from the beginning, through the designated analysis time point(s) (e.g., the Months 6, 12 and 24 study visits) for these above mentioned analyses. Treatment differences in the rates of CSBPAR will also be performed using a per protocol efficacy dataset.
  - This is defined as the set of all data derived from that subset of subjects once treated, are followed up consistently with all study criteria to the extent that no relevant protocol deviations have been identified.

The primary analysis will be done on the ITT population and the sensitivity analyses on the primary endpoints will be done in the As Treated, as well as the Per Protocol population.

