6.2 Populations for Analyses

- The “Intent-to-Treat” (ITT) population includes all subjects who are randomized, transplanted and treated with at least one dose of thymoglobulin and one dose of study treatment, either belatacept or TAC. Subjects will be grouped according to the treatment to which they are randomized.
- The “As Treated” (AT) population includes all subjects who are randomized, transplanted and treated with at least one dose of thymoglobulin and one dose of study drug, either belatacept or TAC. Subjects will be grouped according to the treatment which they actually received. The “As Treated” treatment group is the same as the “As Randomized” treatment group, except in cases where a subject received a different treatment from the one he/she was randomized to for the entire course of their participation in the study. In this case, the “As Treated” treatment group is set to the treatment the subject actually received. In cases where a subject received different treatments after randomization, then the “As Treated” treatment group is the first treatment received. Safety reporting will be done in the “As Treated” population.
- The “Per-Protocol” (PP) population includes all randomized subjects who do not violate terms of the protocol that might affect key study outcomes. The protocol specific definitions for “relevant” protocol deviations are described in [APPENDIX 2](#).
- The PK population includes subjects who receive at least one dose of belatacept and have at least 1 post baseline sample available for PK analyses.

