7 STATISTICAL ANALYSES

7.1 Modifications to the Analyses Specified in the Protocol

Due to the reduction in sample size resulting from premature termination of enrollment as of 31 December 2016, it has been deemed appropriate to revise selected statistical analyses specified in the study protocol [Section 8](#). The following modifications to and clarifications of the analyses have been made:

- 1) All analyses will be performed for the whole study treatment period (i.e. 24 months), including analyses at 6 or 12 months.

- 2) Treatment differences will be produced only for the endpoints specified in the sections of this SAP itemized below, instead for all study endpoints.
- 3) Analysis of acute rejections:
 - a) The treatment differences in the severity grades and therapeutic modalities will not be calculated.
 - b) The sensitivity analyses using the per-protocol population will be performed if there are at least 10% of subjects with a protocol deviation in either treatment groups.
 - c) The sensitivity analyses using the as-treated population will be performed if there are at least 10% of subjects in either treatment group for whom the as-randomized treatment group is different from the as-treated treatment group.
 - d) The sensitivity analysis using right censoring at the time of discontinuation from assigned therapy will not be produced. Acute rejections occurring more than 56 days after the last dose date will be flagged in the listing.
 - e) The descriptive summaries by treatment group for cGFR, graft and subject survival, donor specified antibodies, infection and malignancy at Month 12 for subjects with and without AR by Month 6, and at Month 24 in subjects with and without AR by Month 12, will not be produced. The information regarding these parameters will be included in listings that correspond to the specific analyses of these endpoints.
- 4) Analysis of subject and graft survival:
 - a) A listing including all subjects who died or lost their graft will be produced. Corresponding summaries, treatment differences and time to event analysis will be produced if there are at least 5 subjects across treatment groups who died or experienced graft loss during the 24 Month treatment period.
 - b) Any summaries mentioned above, if to be produced, will only be produced for the whole 24 Month treatment period. The corresponding analyses at 6 and 12 months will not be produced.

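### SAP Appendix 2 does not match protocol exclusion 1(f): it counts a B-cell cross match as a deviation and leaves out pre-transplant donor-specific antibodies

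*SAP*

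**What the plan says.** Protocol 3.3.2, exclusion 1(f), reads "Subjects with a positive T-cell lymphocytotoxic cross match or any detectable donor specific antibodies prior to transplantation", and the synopsis repeats it. Exclusion 2(a) lists, among the underlying renal diseases, "Hemolytic uremic syndrome (HUS) / Thrombotic Thrombocytopenic Purpura".

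SAP 6.2 states that the per-protocol population "includes all randomized subjects who do not violate terms of the protocol that might affect key study outcomes" and sends the reader to Appendix 2 for the definitions. Protocol 8.2 describes the per-protocol data as coming from subjects who, once treated, "are followed up consistently with all study criteria to the extent that no relevant protocol deviations have been identified". In Appendix 2, code 3 lists "Subjects with a positive T-cell or B-cell cross match" and code 5 lists "Atypical hemolytic uremic syndrome (HUS) / thrombotic thrombocytopenic purpura". No code from 1 to 7 mentions DSA.

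The Appendix 2 list is used in two places. SAP 7.3 summarises and lists every randomized subject with a relevant deviation. SAP 7.1 item 3(b) says the per-protocol sensitivity analysis of acute rejection "will be performed if there are at least 10% of subjects with a protocol deviation in either treatment groups"; SAP 7.6.1.1 repeats the condition.

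**The concern.** The per-protocol set is a named sensitivity population for the primary endpoint, clinically suspected and biopsy-proven acute rejection (CSBPAR) at 6 months. Its purpose is to show whether the result holds once subjects who should not have been enrolled are set aside.

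Pre-existing DSA bears directly on that endpoint, because protocol 5.3.7 counts antibody-mediated as well as cell-mediated rejection. Table 9-2 keeps the neighbouring immunological-risk items: PRA, desensitization, previous graft loss from rejection, and cross match. Leaving out DSA alone looks like a failure of alignment rather than a judgement that it does not matter. The B-cell item errs the other way, since it labels as a deviator someone who met every enumerated criterion.

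**Working it through.** This is mainly a comparison of texts.

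**Step 1. Compare the criteria.**

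| Item | Protocol 3.3.2 | SAP Table 9-2 |
|---|---|---|
| T-cell cross match positive | Excluded, 1(f) | Code 3 |
| B-cell cross match positive | Not named | Code 3 |
| Detectable pre-transplant DSA | Excluded, 1(f) | No code |
| HUS as cause of renal failure | Excluded without restriction, 2(a) | Code 5, atypical only |

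**Step 2. Follow four kinds of subject through the rules.**

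- T-cell positive: ineligible and flagged. The documents agree.
- B-cell positive, T-cell negative, no DSA, no other breach: eligible under 1(f), but flagged and dropped from the per-protocol set.
- DSA detectable, cross matches negative, no other listed deviation: ineligible, but not flagged and kept.
- DSA detectable together with a positive cross match, PRA of 20% or more, or desensitization: ineligible and flagged through another item.

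The fourth case shows why the two edits belong together. If the B-cell item were deleted without adding DSA, a subject with DSA caught only by the B-cell test would return to the per-protocol set.

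**Step 3. Look for an explanation.** SAP 7.1 sets out the changes to the protocol's analyses, and Appendix 5 gives the SAP's history. Neither mentions these differences. Appendix 5 records alignment with the protocol's language for SAP Section 6, where the population is defined.

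**Step 4. Check whether the data exist.** SAP 7.4.2 includes the B-cell cross match among baseline characteristics, so code 3 can be applied as written. SAP 7.6.2.4 summarises DSA on Day 1, so some DSA result is also available.

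**Step 5. Size, for illustration.** Inputs are 35 per group (SAP 6.1) and the planning rates in SAP 5. As a check on the exact (Clopper-Pearson) method, the plan's own intervals reproduce: 3.8% of 35 gives 0.2% to 16.4%, and 3% of 35 gives 0.1% to 15.1%.

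- Expected events per group: 0.038 × 35 = 1.33 and 0.03 × 35 = 1.05.
- Per-protocol trigger: 0.10 × 35 = 3.5, so 4 subjects (4/35 = 11.4%); 3/35 = 8.6% falls short.
- Removing one event-free subject when there is one event: 1/35 = 2.86% becomes 1/34 = 2.94%. The exact 95% upper limit goes from 14.9% to 15.3%.
- Removing five event-free subjects (an assumed upper range): 1/30 = 3.3%, upper limit 17.2%.
- Removing the one subject who had the event: 1/35 = 2.86% becomes 0/34 = 0%, a shift of 2.9 points. The upper limit falls from 14.9% to 10.3%.

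**The case against.** The strongest reply is that Table 9-2 was never meant to mirror the exclusions. SAP 6.2 and 7.3 restrict it to deviations that could affect outcomes, and it also omits hepatitis, HIV, tuberculosis, malignancy and the laboratory limits. That stands as a general principle. It is enough to reduce the HUS difference to a wording mismatch, since nothing in the documents ties non-atypical HUS to rejection. It does not cover the B-cell item, because a subset of the protocol's terms cannot contain something that is not one of them. Nor is it a credible reason to omit DSA when the endpoint is rejection.

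A second reply is that protocol 3.3 speaks of a positive lymphocytotoxic cross match without naming a cell type. It does, but only as an example of higher risk. The operative criterion, in 3.3.2 and in the synopsis, says T-cell. This leaves room for the sponsor to keep the B-cell item with a stated reason.

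A third reply concerns the remedy, and it is sound. Protocol 5.9 says antidonor antibody results are not reported to sites because they do not support interpretation for a single subject. Using Day 1 results as individual flags could mark subjects as deviators on results the investigator never saw. SAP 7.6.2.4 also has a middle category, MFI 1000 to 2000, which may or may not count as detectable. Copying the words of 1(f) into code 3 would leave both questions open.

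A reader might also infer more than the documents support:

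- **That every subject with DSA is kept.** Some would be removed through cross match, PRA or desensitization.
- **That one misclassified subject would switch the per-protocol analysis on or off.** This happens only if a group sits at 3 or 4 deviators. Item 3(b) also says protocol deviation without the word relevant, so its link to Table 9-2 is the natural reading rather than an explicit one.
- **That the rejection rate would move by 2.9 points.** This requires the affected subject to be the one with the event.

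**Conclusion.** The mismatch is real and unexplained. Code 3 flags a B-cell cross match that no enumerated exclusion names, and no code covers the detectable DSA that exclusion 1(f) does name. The first contradicts the SAP's own definition of the per-protocol population. The second leaves in that population subjects whose only breach is the DSA part of 1(f). The HUS wording is a minor inconsistency.

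The impact is small. It reaches the SAP 7.3 deviation table and listing, which are always produced, and the per-protocol sensitivity analysis, which is conditional. The primary analysis is on the ITT population and does not change. The study is descriptive and no statistical tests are planned. The documents do not give the number of affected subjects, so the figures above show what could happen under stated assumptions and are not an estimate.

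**What to change.** Before database lock:

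1. Reword code 3 to follow exclusion 1(f): T-cell lymphocytotoxic cross match or any detectable pre-transplant DSA.
2. State which DSA result decides, the one used for eligibility or the Day 1 sample. State which MFI category in SAP 7.6.2.4 counts as detectable, in particular whether 1000 to 2000 does.
3. In the same edit, remove the B-cell cross match from code 3, or keep it and give the reason in SAP 7.1.
4. As a minor point, bring code 5 into line with exclusion 2(a) on HUS, or say why it is narrower.

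The cost is a few lines of SAP text and an update to the programming of the deviation flags. No new data collection is needed if the Day 1 sample is chosen. If the eligibility result is chosen, the sponsor should confirm that it was recorded; the published screening schedule is incomplete, so this cannot be judged here. Timing matters because the trial is open-label, and changes to per-protocol membership after the data have been seen would be hard to defend.
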